## Brief Summary/Abstract

The primary objective of this study is to investigate the effectiveness of local antibiotic versus placebo in the prevention of infections in open fractures. The study will assess whether local treatment of open fractures with the antibiotic tobramycin (in addition to standard systemic antibiotics) will decrease the risk and rate of infection, time to fracture union, and rate of re-operation. This will be studied using a randomized controlled clinical trial design in adult population of age 18-70 years who present with open fractures. About 133 subjects will be recruited in this study at UVA. There will also be similar studies performed at University of Florida- Jacksonville and Medical University of South Carolina and we will be performing a collaborative site analysis study with those centers and we will be sharing demographic, infection and treatment information (at either 2 or 6 weeks), and any adverse events that occur.

**Note:** Standard protocols at UVA will be followed for systemic antibiotic administration. No specimens will be collected for research purposes. The patient will otherwise receive the standard of care treatment for their fractures.

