**3. How many subjects will be enrolled at all sites? 133**

**4. How many subjects will sign a consent form under this UVa protocol? 133**

**5. Provide an estimated time line for the study. 2 years**

### **Inclusion/Exclusion Criteria**

**1. List the criteria for inclusion**

- Ages 18 – 70 years
- Gustilo Type I,II,IIa open fracture (s)
- Ability to provide informed consent (or proxy consent in cases where subject is temporarily impaired when intubated and sedated)
- Subject should be able to follow up at the scheduled times following surgery
- Subjects who may have compartment syndrome, renal insufficiency, and those who are immunosuppressed regardless of antibiotic administration will also be included in the study
- 

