**2. List the criteria for exclusion**

- Closed fracture
- Severe injury requiring flap coverage or vascular reconstruction (Gustilo-Anderson Type IIIB and C respectively)
- Aminoglycoside allergy
- Presentation greater than 48 hours after injury
- Pathologic fracture
- Preexisting infection in bone with an open fracture
- Patients with multiple trauma involving liver, kidney, or brain
- Pregnancy (self-reported)
- Current status as prisoner

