**2. List the procedures, in bullet form, that will be done for RESEARCH PURPOSES as stipulated in this protocol.**

- Medical record review at baseline and all subsequent study weeks up to 1 year after surgery
- Randomization to Antibiotic ( tobramycin) arm or Placebo before surgery by clinical pharmacy program at UVA.
- Experimental group will have the close wound injected with 80 mg/40mL of tobramycin at the END of surgery
- Control group will have 40 mL 0.9%NS injected into the closed wound at the end of the case
- Follow up at 2 and 6 weeks at the clinic. *These visits to the clinic will coincide with the follow up as in standard of care for open fracture management.*

**3. Will you be using data/specimens in this study that were collected previously, with the use of a research consent form, from another research study? NO**

**4. Will any of the procedures listed in item # 2 have the potential to identify an incidental finding? This includes ALL procedures, assessments and evaluations that are being done for RESEARCH PURPOSES that may or may not be considered investigational. yes**

► IF YES, check one of the following two options:

The examination(s) utilize(s) the same techniques, equipment, etc., that would be used if the subject were to have the examination(s) performed for clinical care. **There exists the potential for the discovery of clinically significant incidental findings.**

- The PI takes full responsibility for the identification of incidental findings:
- The PI will inform the subjects verbally of all incidental findings that are of clinical significance or are of questionable significance.
- A follow-up letter describing the finding should be provided to the subject with instructions to either show the letter to their PC or if the subject has no PCP, the subject should be instructed to make an appointment at UVa or at the Free Clinic.

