4. Do you plan to ask the subjects to do anything, other than answering questions, for the study prior to signing a consent? NO

**5. How will the consenting process take place with either the prospective subject, the subject's legally authorized representative or parent/legal guardian of a minor ( if applicable)?**

HIPPA:

If the individual, obtaining consent, works under the HIPAA Covered Entity consenting is covered under Health Care Operations.

If the individual obtaining consent does not work under the HIPAA covered entity, HIPAA does not apply.

Subjects who are being treated for open fractures at University of Virginia, who agree to participate in the study will be asked to sign an informed consent at the hospital. Subjects will be given ample time to go over the informed consent, and an opportunity will be provided to ask questions. Subjects are also allowed to discuss with family and relatives before they sign the consent. Anywhere, from one hour to one week may pass between written consent and initiation of study procedures.

If subject is unresponsive or intubated, and cannot adequately answer the questions and if it is determined that the patient's level of cognition is not likely to change before surgery, a legally authorized representative (LAR) will be approached for proxy consent. Guidance will be provided to assist the LAR in making consent decision. They will be advised to base the decision on the patient's expressed wishes, or, what they believe the patient would have desired under the circumstances of the injury. His or her beliefs and values. When participant regains capacity to consent during the study period, the participant will be re-consented using standard consenting procedures as described below.

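### Pregnancy is excluded by self-report only, yet subjects enrolled by proxy are by the plan's own condition not expected to report anything before surgery, and no other source is named.

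*Combined protocol and SAP*

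**What the plan says.** Inclusion/Exclusion Criteria, item 2, lists "Pregnancy (self-reported" among the exclusions. It is the only entry in that list tied to self-report; aminoglycoside allergy, for example, carries no restriction on where the information comes from.

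Item 1 of the same section sets the age range as "Ages 18 – 70 years", and Human Participants admits both sexes. Item 1 also accepts "proxy consent in cases where subject is temporarily impaired when intubated and sedated".

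Appendix: Recruitment, item 5, gives the procedure. "If subject is unresponsive or intubated, and cannot adequately answer the questions", and if capacity is judged unlikely to change before the operation, then "a legally authorized representative (LAR) will be approached for proxy consent". The representative is guided to decide on the basis of the patient's wishes, beliefs and values. Later, "When participant regains capacity to consent during the study period, the participant will be re-consented using standard consenting procedures".

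On data sources, the Brief Summary/Abstract states "No specimens will be collected for research purposes". Biomedical Research, item 2, lists "Medical record review at baseline and all subsequent study weeks up to 1 year after surgery" among the research procedures.

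**The concern.** An eligibility criterion needs a source that can be consulted for everyone it applies to. Here the plan names one source, the subject's own statement, and separately admits subjects who cannot make one. The criterion therefore directs staff to information that this group cannot supply.

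What is at stake is participant protection. A pregnant woman enrolled by proxy could be randomised and injected although the plan means to exclude her, because nobody was assigned to look anywhere else. The setting makes an unassigned check easy to miss: Appendix: Recruitment, item 7, expects some patients to need resuscitation in intensive care before surgery, and the answer that follows describes open fractures as surgical emergencies.

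**Working it through.** The plan gives no figure on this point and no arithmetic is needed. The check sets the sections side by side.

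1. **Can the proxy group include women who may be pregnant?** Yes. Both sexes are eligible from age 18 (Human Participants; inclusion list), and proxy enrolment is not limited by sex or age.

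2. **Can a proxy-enrolled subject be expected to self-report in time?** No. Appendix: Recruitment, item 5, makes proxy consent conditional on the subject being unable to answer adequately and on capacity being unlikely to change before surgery. Statistical Considerations, item 1, and Biomedical Research, item 2, place randomisation before surgery, and the latter places the injection at its end. So the condition for proxy entry is also a condition under which self-report before randomisation is not expected.

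3. **Does re-consent repair this?** Not reliably. It follows the return of capacity during the study period, which may be after the injection, and the text does not say that eligibility is checked again.

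4. **Does the representative supply the information?** Not as written. The representative's role in item 5 is the consent decision. The Appendix on safeguards for the cognitively impaired confirms that a surrogate will be used but adds nothing on pregnancy status.

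5. **Does a test or record check supply it?** Not as written.
   - The research procedures (Biomedical Research, item 2) include no pregnancy test, and no research specimens are collected.
   - The urine and blood items in the Data and Safety Monitoring Plan, section 2.2, concern renal function.
   - Section 1.5 of that plan treats a pregnancy that occurs as an adverse event, which is not a screening step.
   - A baseline record review is planned, but no section makes it the eligibility check for pregnancy.

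6. **How many subjects are affected?** This cannot be calculated. The documents give neither the share enrolled by proxy nor its sex and age mix. The exclusion of patients whose multiple injuries involve the liver, kidney or brain, and of Gustilo-Anderson IIIB and IIIC injuries, narrows the group. It does not empty it, since the inclusion list still provides expressly for intubated and sedated subjects.

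**The case against.** The strongest reply is that the bracketed source may mean only that no research test is required, which fits a study that collects no research specimens. On that reading a known pregnancy excludes however it becomes known. It could become known through the baseline record review, the representative, a statement made before sedation, a routine clinical test, or the treating clinicians who approach patients (Appendix: Recruitment, item 2c). This stands in part. A reader might infer that silence counts as passing the criterion, so that pregnant women would be enrolled unnoticed. The documents do not support that: several routes could bring a pregnancy to light. What remains is that none of them is written down as the check.

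On timing, some wounds are closed only at a later operation (Appendix: Recruitment, item 7). In those cases capacity, and re-consent, might return before the injection. That helps some subjects but is not a planned eligibility step, and randomisation could already have taken place.

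Two stronger readings are tempting and should be resisted.

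- **A count.** If one assumes that 10% to 20% of the 133 subjects enter by proxy and that a quarter to a third of those are women of childbearing age, then 133 × 0.10 × 0.25 = 3.3 and 133 × 0.20 × 0.33 = 8.8, or about 3 to 9 women. Every share is assumed and none can be checked in the documents. The result also counts women without a self-report, not pregnancies, which would be far fewer.
- **An analysis problem.** The sample-size section implies 60 × 0.10 + 60 × 0.01 = 6.6 expected infections, so a reader might infer that removing an ineligible subject after randomisation could disturb the primary result. No section says that ineligible subjects are removed, so this consequence is speculative.

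It is also fair to say that the plan gives no reason for the exclusion, and that its risk table (Data and Safety Monitoring Plan, section 2.1) names no pregnancy or foetal risk. The documents therefore offer no basis for sizing harm.

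**Conclusion.** The concern holds as a gap between three parts of the plan. The exclusion relies on self-report alone. The inclusion list and the consent procedure admit subjects who, by the plan's own condition, are not expected to report anything before surgery. No available section names another source for the eligibility check.

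This is more than a missing detail, because the rule as written points staff to the one source that these subjects cannot provide. Its extent is likely small but cannot be calculated. Alpha, power, sample size and the primary comparison are not affected.

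The conclusion rests on reading the bracketed words as the named source, and on the text available for review; some pages, including the consent pages, were not available. The gap should be closed because it concerns subjects who cannot speak for themselves and the repair is cheap. It is not a flaw that threatens the trial.

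**What to change.** Reconcile the inclusion list, the exclusion list and Appendix: Recruitment, item 5. Amend the pregnancy criterion so that self-report applies to subjects who can answer. For subjects enrolled by proxy, pregnancy status would be taken from the legally authorised representative's report or from a pre-operative result already in the chart. No new test is needed, since the baseline record review is already planned. Add a matching line to the eligibility form recording which source was used.

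The plan should also state what happens when neither source is informative. Barring such women from proxy enrolment would be a new eligibility rule, so that decision belongs to the investigator and the IRB.

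The cost is one amended line and one added eligibility check. The downside is that a few proxy-consented women may not be enrolled.

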**3. List any restrictions on use of other drugs or treatments.**

Any other antibiotic not related to open fracture is prohibited during the study, which could mask wound infection.

### **Statistical Considerations**

**1. Is stratification/randomization involved? Yes**

► IF YES, describe the stratification/ randomization scheme.

Subjects will be randomized prior to surgical treatment. Randomization will be double blind. Neither the subject nor the surgeon injecting the antibiotic or placebo know which arm the subject belongs to. The Medical Pharmacist or [name] will have the key to randomization, at UVA. The other sites involved will be expected to manage their randomization scheme. UVA will not oversee the other sites.

► IF YES, who will generate the randomization scheme?

Other: [name]

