**2. What are the statistical considerations for the protocol?**

- This is a prospective, randomized double blind study. Subjects will be randomized to antibiotic (80mg tobramycin/40mL saline) or placebo arm (40mL of 0.9% saline).
- The primary objective of this study is to evaluate the efficacy of local antibiotics in decreasing incidence of infection. The primary outcome will include evidence of infection in the first 6 weeks of surgery. Infection will be defined as major and minor, with major indicated by return to the operating room for irrigation and debridement. Minor infection is represented by documentation of cellulitis or superficial infection at surgical site and administration of oral antibiotics. .
- Superficial infection as indicated by documentation of cellulitis at surgical site and administration of oral antibiotics with the indication of wound problems. The primary purpose of this study is to document infection rates in the first 6 weeks after surgery. If an infection is found, it will be cared for per standard clinical care; however, it will not be followed for research purposes.
- There will be no contingencies for early stopping as the patients are receiving a single dose of antibiotics. There will be no interim analysis or stratification factors
- We expect approximately - 60 – 65 open fractures within a year to be treated at UVA based on historical records.

We will use a one-sided test for proportions to compare the control and experimental groups for the primary endpoint (presence of infection) and the secondary endpoint of evidence of non-union. A p-value less than 0.05 will be considered a significant result.

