**3. Provide a justification for the sample size used in this protocol.**

A sample size analysis was completed for different alpha and power levels. A one-sided test for proportions was chosen to compare the baseline (no treatment) group to the hypothesized proportion (treatment group); based on historical data, we assumed that the no treatment group would have a 10% infection rate, and the treatment group would have a 1% infection rate. Using an alpha of 0.05 and power of 70%, we would need to have 60 patients in each group.

With an expected accrual rate of 65 patients per year, we would expect to enroll 130 patients in two years. In order to maintain the sample size needed to ensure statistically valid results, we would want to enroll approximately 133 patients over the study period to end up with at least 120 patients in the analysis.

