**6. Have you been working with a statistician in designing this protocol? Yes**

IF YES, what is their name? [name]

Will data from multiple sites be combined during analysis? Yes

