### INSTRUCTIONS

- e.g. weekly conference calls, use of SAE forms, overall safety monitor etc.

- include frequency of communication
- identify participants ( by role) in this process

Collaborative Site Analysis Studies DSMP			
Type of Event	To whom will it be reported:	Time Frame for Reporting	How reported?
*Serious, unexpected and related or possibly related adverse events	All Research Sites	Within 15 days after the site PI receives knowledge of the event.	IND/IDE Safety Report (Cover letter, copy of MedWatch/narrative)
*Unanticipated Problem	All Research Sites	Within 15 calendar days from the time the Site PI receives knowledge of the event.	Letter to Participating PIs, Copy of MedWatch or narrative
Protocol Violations/Noncompliance The IRB-HSR only requires that MAJOR violations be reported, unless otherwise required by the sponsor.	All Research Sites	Within 7 calendar days from the time the study team received knowledge of the event.	Protocol Violation, Noncompliance and Enrollment Exception Reporting Form http://www.virginia.edu/vprgs/irb/hsr_forms.html Go to 3 rd bullet from the bottom.

\*as defined in each sites protocol

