**4. How will the endpoint data be collected/recorded.**

  X   Protocol specific case report forms

Source documents

Database:  Specify  Answer/Response:

Other:  Specify  Answer/Response: excel spreadsheet with de-identified data from other institutions will be combined with the excel spreadsheets at UVA. The University of Virginia will not be transferring data to other institutions, only receiving data.

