**5.2. What is the composition of the reviewing body and how is it affiliated with the sponsor?**

Information may be found in the UVa Cancer Center Institutional DSMP  
 Collaborative Site Analysis Study- see CSAS section of this DSMP  
 Other: Specify Answer/Response:

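### Separately randomised sites will be combined but the only stated test is unstratified: stratify any pooled comparison by site, a low-cost guard against confounding the documents neither show nor exclude

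*Combined protocol and SAP*

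**What the plan says.** Statistical Considerations, item 1, places randomisation outside UVA in the hands of each site: "The other sites involved will be expected to manage their randomization scheme. UVA will not oversee the other sites". The Brief Summary describes similar studies at two other centres whose data are to be analysed together with UVA's. No allocation ratio is stated for any site. Equal groups appear only through the sample size in item 3: "we would need to have 60 patients in each group".

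Combining the data is stated twice. Item 6 reads "Will data from multiple sites be combined during analysis? Yes", and the Data and Safety Monitoring Plan, item 4, says that an "excel spreadsheet with de-identified data from other institutions will be combined with the excel spreadsheets at UVA".

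The analysis is given in item 2: "We will use a one-sided test for proportions to compare the control and experimental groups for the primary endpoint". Item 4 repeats it, and item 5 says that only a primary analysis is planned. Item 2 also says that there are no stratification factors. No section provides for a site term, a site-stratified sensitivity analysis or a ratio that outside sites must use.

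**The concern.** Patients are randomised within a site, so the comparison that randomisation protects is the one within sites. Collapsing the sites into one two-by-two table is safe only if the share of patients given placebo is unrelated to the underlying infection risk across sites. A common ratio would secure that, but UVA says that it will not oversee the other sites' schemes.

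If higher-risk sites gave relatively more placebo, tobramycin would look protective with no true effect, and the one-sided error would exceed 5%. In the reverse pattern a real benefit would be partly hidden. Few infections are expected and one test carries the efficacy conclusion, so a false difference of one or two percentage points matters.

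**Working it through.** **The plan's own figure.** Item 3 assumes 10% against 1%, one-sided alpha 0.05 and power 70%. With mean risk 0.055:

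n = [1.645 × √(2 × 0.055 × 0.945) + 0.524 × √(0.10 × 0.90 + 0.01 × 0.99)]² / 0.09² = [1.645 × 0.3224 + 0.524 × 0.3161]² / 0.0081 = 59.8, so 60 per group.

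The stated figure reproduces, for two equal groups treated as one population.

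**Inputs that the documents do not give.** Site sizes, site ratios and site risks are all assumptions below. Two layouts are used: UVA supplying 120 with others added, and 120 in all.

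**How the distortion arises.** Take no treatment effect, risk 5% at UVA (60 placebo, 60 tobramycin) and 15% elsewhere (40 placebo, 20 tobramycin).
- Placebo: (60 × 0.05 + 40 × 0.15) / 100 = 9 / 100 = 9.0%
- Tobramycin: (60 × 0.05 + 20 × 0.15) / 80 = 6 / 80 = 7.5%
- False benefit: 1.5 points

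With 30:30 elsewhere, both arms are (3 + 4.5) / 90 = 8.3%, and the false benefit is zero.

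**Tests compared.** All reject at one-sided 5%.
- Crude z: difference in pooled proportions divided by √[p̄(1 − p̄)(1/n_P + 1/n_T)], no continuity correction.
- Fisher: one-sided exact test on the collapsed table.
- CMH: z = Σ(a − E) / √ΣV over sites, where a is the placebo infections, m all infections, E = m·n_P/N and V = n_P·n_T·m(N − m) / [N²(N − 1)].

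**One-sided error with no treatment effect, by full enumeration** (ratios are placebo:tobramycin):

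| UVA | Others | Risks, UVA / others | Crude z | Fisher | CMH |
|---|---|---|---|---|---|
| 60:60 | 40:20 | 5% / 15% | 8.54% | 5.38% | 4.83% |
| 60:60 | 36:24 | 5% / 15% | 7.03% | 4.52% | 4.86% |
| 60:60 | 20:40 | 5% / 15% | 2.14% | 1.00% | 5.27% |
| 60:60 | 30:30 | 5% / 15% | 5.01% | 2.63% | 5.11% |
| 60:60 | 20:10 and 10:20 | 5% / 15% | 5.01% | 2.63% | 5.01% |
| 40:40 | 27:13 | 5% / 15% | 7.26% | 4.07% | 4.63% |
| 40:40 | 13:27 | 5% / 15% | 2.86% | 1.07% | 5.45% |
| 40:40 | 20:20 | 5% / 15% | 5.10% | 2.38% | 5.22% |
| 60:60 | 40:20 | 8% / 12% | 5.98% | 3.60% | 4.87% |
| 60:60 | 40:20 | 10% / 10% | 4.66% | 2.74% | 4.85% |

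The crude z test leaves its level only where ratio and risk are associated. A more extreme layout was simulated: sites of 60, 30 and 30, tobramycin:placebo 2:1, 1:1 and 1:2, risks 5%, 10% and 20%. It gave 14.8% for crude z and 4.9% for CMH.

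**Power at 10% against 1% in every site.**
- UVA 40:40, others 20:20: 80.2% for both tests. This exceeds the 70% of the formula because that is a normal approximation, and only 6 and 0.6 infections are expected per 60 patients.
- UVA 40:40, others 13:27: 79.5% crude, 77.2% CMH.
- UVA 40:40, others 27:13: 71.6% crude, 73.4% CMH.
- Simulated, sites of 60, 30 and 30, tobramycin:placebo 2:1, 1:1, 1:2: 76.0% crude, 73.6% CMH. With 2:1, 1:1, 1:1: 81.8% crude, 77.5% CMH.

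**The case against.** The strongest reply is that nothing has been shown to go wrong. The harm needs unequal ratios, unequal risks and an association between them. The one piece of evidence on ratio, the equal groups in item 3, points to 1:1. The 8.5% needs a threefold risk difference and 2:1 placebo at every outside site. The plan does not name the test variant, and with Fisher's test only one row of the table passes 5%. All of this stands. A reader might infer that the sites use different ratios, or that the pooled result will be biased; the documents support neither.

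It is also open whether the powered test is pooled at all. Item 3 reasons from UVA accrual ("With an expected accrual rate of 65 patients per year", in line with the UVA estimate in item 2), so the primary test could be meant for UVA alone. Item 6 still says that data will be combined in analysis, without saying how.

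Two pieces of text carry less than they may seem to. The words "as defined in each sites protocol" are a footnote to the safety-reporting table and point to separate site protocols only indirectly. The options in the Data and Safety Monitoring Plan, item 5.2, have lost their selection marks and prove nothing here. The statement about no stratification factors may concern randomisation rather than analysis, but the named test has no site term on either reading.

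Finally, stratifying is not free, asymptotic CMH sits slightly above 5% in some rows, and UVA cannot simply impose 1:1 on sites it does not oversee. These objections stand and shape the fix. They do not explain why patients randomised separately should be compared as if randomised together.

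**Conclusion.** The concern holds as an unguarded condition, not as a demonstrated error. Separate randomisation without oversight, the absence of a stated common ratio, planned combination of the data and an unstratified test are all in the text. An association between ratio and risk is not.

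If such an association existed, the size would depend on assumptions: crude z error of 8.5% with risks of 5% and 15% and others at 40:20, 6.0% with risks of 8% and 12%, and near 2% to 3% in the reverse pattern. Under 1:1 everywhere it is 5.0% to 5.1%. CMH stayed between 4.63% and 5.45% throughout the table. The case for change rests on the missing pooling specification, and not on the largest of these figures. It is a cheap improvement that should be made.

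The two uses of 133, the wording on 2 or 6 weeks, and missing data are separate matters and add no weight here.

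**What to change.** In Statistical Considerations, items 2 and 4, state that any primary comparison that pools sites is a one-sided CMH test stratified by site at the 0.05 level, reported with a site-stratified risk difference and its confidence interval. If strata are expected to be sparse, name an exact stratified test instead. Make that choice before treatment codes are released. With 120 patients at 1:1 the exact stratified test has about 56% power at 10% against 1%, the same as Fisher's test, against about 80% for the uncorrected asymptotic tests. That loss comes from the exact method and not from stratifying.

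In item 1, make pooling conditional on obtaining and recording each contributing site's allocation ratio and randomisation method. This does not require UVA to oversee those sites. It matters because stratifying cannot repair poor concealment within a site.

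**Cost.** Protocol wording, a site column in the combined spreadsheet and one request to each site. The section on information from outside institutions suggests that a protocol modification may be needed for the request. There is no power cost when all sites use 1:1. Where ratios differ but risks do not, the loss was about 2 to 4 points in some layouts, with a small gain in another.
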